#### **9.1.4. Expected Adverse Events**

Based on our own experience and the published literature ([Table 1](#)), we expect that gastrointestinal symptoms (including fever, aspiration, belching, bloating, nausea or vomiting, gastroesophageal reflux, abdominal cramps, abdominal pain, diarrhea, constipation) may be common post administration of all three investigational products, both as a consequence of the underlying disease being treated, and potentially as an adverse effect of the administered product.

To distinguish a causal relationship between these AEs and the investigational product, we will set a threshold of  $\geq 50\%$  increase in gastrointestinal symptom severity (e.g., number of stools or volume of diarrhea; number of vomiting episodes or hours/day of nausea) as compared to symptom severity in the 48-hour period surrounding the intervention.

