### **3.2.3.1. Post-PMT Administration monitoring: Bedside for 60 Minutes**

Safety endpoints for all routes of administration will include worsened abdominal pain, fever, tachycardia, and hypotension ([Section 3.2.1](#)). Safety endpoints for upper enteral delivery (i.e., PMT-002 or PMT-003) will include evidence of aspiration (including reduced oxygen saturation, tachypnea, or respiratory distress, as defined above).

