### 9.1.3. Adverse Events of Special Interest (AESI)

Based on prior published experience with FMT-associated risks (Table 1), we have defined several adverse events of special interest.

In the initial, 60-minute bedside observation period following administration of investigational product, subjects will be monitored with close attention to the following:

- allergic reaction (temperature, skin rash, heart rate, or blood pressure change as already described) -- PMT-001, 002, and 003
- sepsis or shock (temperature, heart rate, or blood pressure change as already described) – PMT-001, 002, and 003
- bowel injury (abdominal pain change as already described) – PMT-001, 002, and 003
- aspiration (respiratory rate or oxygen saturation change as already described) – PMT-002 and 003 only

In the subsequent, 7-day monitoring period following administration of investigational product, subjects will be monitored with close attention to the following:

- donor-derived infection (temperature or abdominal pain change as already described) – PMT-001, 002, and 003
- worsening CDI (temperature, change in stool frequency/quantity or abdominal pain, or emesis as already described) – PMT-001, 002, and 003

In the subsequent, 30-, 90-, and 180-day monitoring periods, subjects will be monitored with close attention to the following:

- transmitted infection (temperature or abdominal pain change as already described) – PMT-001, 002, and 003
- recurrent CDI (temperature, change in stool frequency/quantity or abdominal pain, or emesis as already described) – PMT-001, 002, and 003
- metabolic changes (polydipsia, polyuria, weight gain, or weight loss) – PMT-001, 002, and 003

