### ***12.1. Risks***

The main risks of this study are related to administration of the investigational product. The most severe possible risks include: allergic reaction, donor-derived infection, aspiration (for upper gastrointestinal administration), bowel perforation (for lower gastrointestinal administration), and death. Other risks include: nausea, vomiting, abdominal pain, diarrhea, flatulence, fever. Product specific risks are described in [Section 9.1.4](#).

Theoretical long-term risks may include: changes in metabolism, weight changes, development of autoimmune conditions.

Other risks include loss of privacy or confidentiality, as a result of study staff interacting with subjects.

These risks will be discussed with subjects during the informed consent process. The eligibility criteria will help mitigate these risks (e.g., excluding subjects with neutropenia or bowel perforation, and not permitting subjects at risk for aspiration to receive investigational product via upper gastrointestinal delivery). To minimize the risk of privacy and confidentiality loss, the minimum number of required study staff will interact with subjects, and all collected data will be protected as above.

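### Section 9.1.4 lists aspiration as expected after all three products with no seriousness limit, which conflicts with other sections and leaves unclear whether a serious case triggers the first halt rule and the expedited FDA reports

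*Combined protocol and SAP*

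**What the plan says.** Section 9.1.4 (Expected Adverse Events) gives one pooled list. It states that "we expect that gastrointestinal symptoms (including fever, aspiration, belching, bloating, nausea or vomiting, gastroesophageal reflux, abdominal cramps" and the remaining listed symptoms "may be common post administration of all three investigational products". It attributes them to the underlying disease and possibly to the product. No entry carries a grade or seriousness limit.

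Other sections treat aspiration differently:

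- Section 9.1.3 (events of special interest): "aspiration (respiratory rate or oxygen saturation change as already described) – PMT-002 and 003 only".
- Section 3.2.3.1 (bedside safety endpoints): "Safety endpoints for upper enteral delivery (i.e., PMT-002 or PMT-003) will include evidence of aspiration".
- Section 3.1.3 (bedside monitoring) labels the watch for aspiration as applying to PMT-002 and PMT-003.
- Section 12.1 (Risks): "The most severe possible risks include: allergic reaction, donor-derived infection, aspiration (for upper gastrointestinal administration), bowel perforation", with death completing that group. A lower tier follows: "Other risks include: nausea, vomiting, abdominal pain, diarrhea, flatulence, fever". It then adds "Product specific risks are described in" Section 9.1.4, although that section does not separate the products.

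Section 9.4 contains two halt rules. The first needs an event that is serious, unexpected and related to the product. The second needs a product-related infection and does not mention expectedness. Section 9.3 contains two expedited FDA reports, one within 7 days for fatal or life-threatening reactions and one within 15 days for other serious related events. Both apply only if the event is unexpected.

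**The concern.** There are two separate points.

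**Product scope.** Four sections tie aspiration to upper delivery. Section 9.1.4 extends it to the enema product as well, and it is the section that 12.1 names for product-specific information.

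**No seriousness limit.** This is the point that matters, and it concerns upper delivery only. The protocol does not define 'unexpected'. An assessor who looks in the protocol for what counts as expected finds only 9.1.4, where aspiration is listed by name. If a serious, related, non-infectious aspiration after PMT-002 or PMT-003 is classed from that list, the immediate pause and the expedited FDA report would not be triggered. Those are the two fastest responses the protocol provides. They would be lost for a risk that 12.1 places in its gravest tier, with products for which 1.2.2 reports no prior clinical research data.

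**Working it through.** No power or sample-size arithmetic applies. The check is to set the sections side by side and follow one case through the rules.

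**Step 1. Product scope.** Section 9.1.4 covers 3 of 3 products. Sections 3.1.3, 3.2.3.1 and 9.1.3 name 2 of 3 (PMT-002 and PMT-003), and 12.1 says the same by route. The texts differ on PMT-001.

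**Step 2. Where aspiration sits among the listed events.** Section 9.1.4 has 10 entries: fever; aspiration; belching; bloating; nausea or vomiting; reflux; cramps; abdominal pain; diarrhea; constipation. Section 12.1 names 5 gravest risks (the 4 in the quote above, plus death).

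- In the gravest tier of 12.1: aspiration only, 1 of 10.
- In the lower tier of 12.1: fever, nausea or vomiting, abdominal pain, diarrhea, 4 of 10.
- In neither tier: belching, bloating, reflux, cramps, constipation, 5 of 10.
- Check: 1 + 4 + 5 = 10.

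Aspiration is therefore the one entry that the protocol itself both calls expected and ranks among its gravest risks.

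**Step 3. Stated basis for listing it.** Section 9.1.4 cites the team's own experience and Table 1. Eight of the 10 entries appear in a Table 1 risk cell; aspiration and reflux do not. Five Table 1 studies used an upper route at least in part (one duodenal tube, one oral, one oral or colonoscopy, two mixed-route case series: 1 + 1 + 1 + 2 = 5), and aspiration is named in 0 of 5. This does not refute 9.1.4, because the team's own experience remains a stated basis.

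**Step 4. Is expectedness settled elsewhere in the protocol?** The six items that 9.2 requires for each adverse event do not include expectedness. Neither do the contents of the initial serious-event notice in 9.3. Section 9.4 uses the term without a definition.

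**Step 5. Follow a serious, related, non-infectious aspiration after PMT-002 or PMT-003.**

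| Rule | Needs 'unexpected'? | If classed expected | If classed unexpected |
|---|---|---|---|
| Halt rule 1 (9.4) | Yes | Not triggered | Triggered |
| 7-day FDA report (9.3) | Yes | Not triggered | Triggered if fatal or life-threatening |
| 15-day FDA report (9.3) | Yes | Not triggered | Triggered otherwise |
| Halt rule 2 (9.4) | No | Not triggered (no infection) | Not triggered (no infection) |
| Sponsor notice in 24 hours (9.3) | No | Applies | Applies |
| IRB reporting (9.3) | Not stated as a condition | Per local requirements | Per local requirements |

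Three rules depend on the classification. Any one event would use one of the two FDA routes, so a single case classed as expected would lose two responses: the pause and the report that fits it.

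**The case against.** The strongest reply is that the protocol never says 9.1.4 governs 'unexpected' in 9.3 and 9.4. The trial commits to 21 CFR Part 312, and it has a separate Drug Safety Monitoring Plan and a DSMB Charter. None of these can be read here, and any of them may set the reference. This stands, and it makes the harm conditional. It does not remove the point, because the protocol cites none of them as the reference for the term.

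Second, 9.2 asks for events to be recorded as diagnoses where possible, graded, and assessed for seriousness and relatedness. A respiratory diagnosis following aspiration need not match an entry in a list of gastrointestinal symptoms, and infection goes to halt rule 2. This narrows the exposed case to a serious non-infectious event recorded as aspiration, which is an entry on the list.

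Third, the scope conflict has little consequence of its own. Section 9.1.4 allows that events may come from the underlying disease, and 6.2.3 watches for aspiration without a product limit. This is fair: that half of the point is a wording alignment.

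Fourth, the missing limit affects all 10 entries, so one definition of 'unexpected' would be the more general repair. That is true. Aspiration is singled out only because of the overlap in Step 2.

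A reader might go further and infer that the 9.1.4 causality threshold, a 50% or greater "increase in gastrointestinal symptom severity (e.g., number of stools or volume of diarrhea; number of vomiting episodes or hours/day of nausea"), leaves aspiration with no route to being judged related. The documents do not support that. The measures are given as examples, and 9.2 requires a relatedness judgement for every adverse event.

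In the other direction, a reader might count the statement in 12.1 that subjects at risk of aspiration will not receive upper delivery as a working safeguard. Section 12.1 credits this to the eligibility criteria, but no such criterion appears in 4.1, 4.2 or the allocation rules in 3.1.6.

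**Conclusion.** The point holds as a minor safety clarification. The conflict in product scope is plain on the text. The consequence for the halt and reporting rules is conditional: it assumes that an assessor takes 9.1.4 as the reference for expectedness and that no separate document overrides it. On that assumption, the first halt rule and both expedited FDA reports would not be triggered by a serious, related, non-infectious aspiration after upper delivery.

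A reader might infer that the protocol exempts aspiration from its stopping rule, or that such a case would go unseen. Neither follows. The protocol leaves the classification open. Bedside checks, tracking as an event of special interest (whose frequency is a primary safety endpoint), 24-hour sponsor notice, IRB reporting, Medical Director oversight and DSMB review continue however the event is classed. The realistic harm is a delayed pause or report.

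The documents give no aspiration rate, so no probability can be attached. A reader might multiply the 30 subjects planned for the upper arm by three doses to obtain a maximum exposure of 90. That is not a true maximum: 30 is a target, 6.2.4 allows a change of formulation at repeat dosing, and 3.1.5 provides for repeat enrollment.

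**What to change.** In 9.1.4, either remove aspiration from the list, or limit it to non-serious events after PMT-002 and PMT-003. Either choice also resolves the conflict with 3.1.3, 3.2.3.1, 9.1.3 and 12.1.

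In 9.3 and 9.4, state that serious aspiration counts as unexpected. If the Drug Safety Monitoring Plan already sets a reference that gives this result, cite it in both sections instead. A citation of that kind would also settle the term for the other nine entries.

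The cost is a few lines of protocol wording. The possible downside is an occasional temporary pause for DSMB review after a serious, related aspiration.

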#### **3.1.4. Post-PMT Administration monitoring: Daily for 3 Days after Administration/Enrollment**

The subject will be monitored every calendar day for three days after each PMT administration in order to assess their eligibility for repeat up to 2 additional doses of PMT at 3 days after the first administration and 3 days after a second administration (if given), as well as to assess for adverse events. If the subject continues to meet criteria for severe or severe-complicated disease within the prior 24 hours at 3 days after the initial administration and then 3 days after the second administration (if given), the subject will be eligible for a repeat dose of PMT (same formulation as per initial randomization). If PMT administration is unable to be performed at 3 or 6 days following the first administration, then administration within 1 calendar day before or after those days will be permitted. Assessment for eligibility for an additional dose will be performed on the day of repeat administration. For subjects in the non-PMT arm, monitoring will be performed daily for three days after enrollment for adverse event assessment.

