#### **3.1.5. Post-PMT Administration Follow-Up**

Following a subject's final PMT administration or enrollment for those in the non-PMT arm, subjects enter the follow up phase. During this phase, the following will occur: (1) while remaining inpatient, daily maximum temperature, number of bowel movements, and any episodes of emesis will be recorded (based on electronic medical record) for 7 calendar days post-FMT or post-enrollment for the non-PMT arm; (2) in preparation for discharge from the hospital, subjects will record daily temperature, number of bowel movements, and any episodes of emesis for 7 days post last FMT/post-enrollment (subjects will be given a symptom diary card; a digital thermometer will also be provided); (3) subjects will be contacted by telephone or in-person for an interview focused on potential adverse events at 7 days (or next working day, not to exceed 10 days) after final FMT or after enrollment for non-PMT arm; (4) subjects will be contacted by telephone or in-person at 30 days (+/- 3 days) after final FMT or after enrollment for non-PMT arm for an interview focused on potential adverse events; (5) subjects will be contacted by telephone or in-person at 90 days (+/- 7 days) after final FMT or after enrollment for non-PMT arm for an interview focused on potential adverse events; (6) subjects will be contacted by telephone or in-person at 180 days (+/- 7 days) after final FMT or after enrollment for non-PMT arm for an interview focused on potential adverse events.

Telephone versus in-person follow-up will be determined based on subject preference. (If subjects prefer to be seen in person, but have been discharged from the hospital, a clinic visit with a study team member will be arranged). All FMT recipients (or their surrogates) will be given contact information for the study coordinator. As detailed above, subjects will be followed for 180 days following last investigational product administration or after enrollment for non-PMT arm. All subjects will be also provided a study contact telephone number on a copy of the

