### **6.3. Study Follow-up Phase**

#### **6.3.1. Follow-up 7 days**

Following a subject's final PMT administration or following enrollment in the non-PMT arm, subjects enter the follow up phase. During this phase, vital signs, symptoms, and laboratory values suggestive of adverse events will be tracked and recorded. Specifically, while remaining inpatient, daily maximum temperature, number of bowel movements, and any episodes of emesis will be recorded (based on electronic medical record) for 7 calendar days post-FMT or post-enrollment in non-PMT arm. In preparation for discharge, subjects will be given a diary for tracking daily temperature, number of bowel movements, and any episodes of emesis for 7 days post last FMT or post-enrollment (subjects will be given a symptom diary card; a digital thermometer will also be provided). Subjects will be contacted by telephone or in-person for an interview focused on potential adverse events at 7 days after final FMT or post-enrollment for non-PMT arm; the first attempt at contact will be made by the first working day at 7 days or later (not to exceed 10 days) following the final FMT. (In case of telephone follow-up, the 7-day symptom diary card will be transcribed by study staff over the phone/and or collected during the in-person follow-up visit. See [Section 6.3.2](#)). Telephone versus in-person follow-up will be determined based on subject preference. If subjects prefer to be seen in person, but have been discharged from the hospital, a clinic visit with a study team member will be arranged.

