#### **9.2. Recording of Adverse Events**

Safety will be assessed by monitoring and recording potential adverse effects using the Common Toxicity Criteria version 5.0 (CTCAE V5.0) at each study visit. Participants will be monitored by medical histories, physical examinations, and other studies. If CTCAE V5.0 grading does not exist for an adverse event, the severity of mild, moderate, severe, life-threatening, and death, corresponding to Grades 1-5, will be used whenever possible.

At each contact with the subject, the investigator will seek information on adverse events by non-directive questioning and, as appropriate, by examination. Adverse events may also be detected when they are volunteered by the subject during the screening process or between visits, or through physical examination, laboratory test, or other assessments. Information on all adverse events will be recorded in the source documentation. To the extent possible, adverse events will be recorded as a diagnosis and symptoms used to make the diagnosis recorded within the diagnosis event.

As much as possible, each adverse event or follow-up information will be evaluated to determine:

1. Severity grade (CTCAE V5.0 Grade 1-5)
2. Duration (start and end dates)
3. Relationship to the study treatment or process – [Reasonable possibility that AE is related: No (unrelated/ not suspected) or Yes (a suspected adverse reaction)]. If yes (suspected) - is the event possibly, probably or definitely related to the investigational treatment?
4. Action taken with respect to study or investigational treatment or process (none, dose adjusted, temporarily interrupted, permanently discontinued, unknown, not applicable)
5. Whether medication or therapy taken (no concomitant medication/non-drug therapy, concomitant medication/non-drug therapy)
6. Whether the event is serious

Once an adverse event is detected, it should be followed until its resolution or until it is judged to be permanent, and assessment should be made at each visit (or more frequently, if necessary) of

any changes in severity, the suspected relationship to the study treatment, the interventions required to treat it, and the outcome.

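### The threshold in section 9.1.4 that is meant to tell product-caused from disease-caused gastrointestinal events uses no control-arm information, so it cannot do that job and its false-attribution rate is uncontrolled

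*Combined protocol and SAP*

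**What the plan says.** Section 9.1.4 (Expected Adverse Events) expects gastrointestinal symptoms to be common after all three products, "both as a consequence of the underlying disease being treated, and potentially as an adverse effect of the administered product". The next sentence sets the rule: "To distinguish a causal relationship between these AEs and the investigational product, we will set a threshold of" at least 50%. The threshold applies to a rise in stools, vomiting or nausea, with number, volume or hours per day given as examples of measures. The reference is the subject's own experience around dosing: "as compared to symptom severity in the 48-hour period surrounding the intervention".

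Four other places bear on it:

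- Section 9.2 (Recording of Adverse Events) asks for a relatedness judgement on each event: "Reasonable possibility that AE is related: No (unrelated/ not suspected) or Yes (a suspected adverse reaction"), graded further if the answer is yes. It does not mention the 50% threshold.
- Section 8.5.4 (Safety Analysis) says that frequencies of AEs, SAEs and AESIs will be described. It names no comparison between arms and no tally of product-related events.
- Section 3.1.5 has daily temperature, bowel movements and emesis recorded "for 7 calendar days post-FMT or post-enrollment for the non-PMT arm". Section 6.3.1 repeats this.
- Section 3.1.4 covers controls as well: "For subjects in the non-PMT arm, monitoring will be performed daily for three days after enrollment for adverse event assessment".

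**The concern.** The rule is asked to separate two causes, but its only inputs are one subject's symptoms around dosing and the same subject's symptoms later. Disease course and ordinary day-to-day variation move those counts whether or not the product does anything. What shows how much they move without the product is the randomized control arm. The rule does not use that arm, and cannot be applied to it because controls have no intervention for the window to surround.

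Three operating details are also missing: the unit compared (one day, a 48-hour window or an average), the length of the comparison period, and what happens when the reference count is zero. The chance of crossing the threshold with no product effect depends heavily on all three.

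Safety of the PMT products is the secondary objective. If the threshold informs which common gastrointestinal events are called product-related, that classification will partly reflect how variable the symptoms are, and no control rate for the same threshold will be available to show it.

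**Working it through.** **No figure to reproduce.** The plan states no error rate for this rule and gives no baseline mean or variance for stool or vomiting counts. The only stool-frequency figure is the resolution criterion of fewer than 8 bowel movements per day in section 3.2.1, which is not a baseline rate. Everything below therefore rests on assumed rates.

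**Inputs from the documents.** Threshold of 50% or more, and a 48-hour reference (9.1.4); 7 days of daily counts (3.1.5, 6.3.1); 30 subjects per arm, so 60 FMT and 30 control (4.5).

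**Assumptions.** Independent daily Poisson counts; two reference days; no product effect; means either stable or falling by 10% or 20% per day. The reference is taken as undisturbed by the product, so the result does not rest on the word surrounding. If the window includes post-dose hours, a true early effect would raise the reference and be partly hidden, which is a further problem.

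**Formula.** Let B be the mean of the two reference days and Y the later quantity (highest single day, highest 48-hour mean, or 7-day mean). A subject is flagged if Y ≥ 1.5 × B and Y > 0.

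**Simulated share flagged with no product effect** (5 stools/day; vomiting 0.3/day where included):

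| Reading of the rule | Stable | Falling 10%/day | Falling 20%/day |
|---|---|---|---|
| Stools or vomiting, any of 7 days, zero reference counts | 92% | 79% | 64% |
| Same, but a zero vomiting reference cannot be flagged | 73% | 52% | 38% |
| Stools or vomiting, any 48-hour window, zero reference counts | 79% | 59% | 44% |
| Stools only, any of 7 days | 61% | 35% | 21% |
| Stools only, any 48-hour window | 43% | 19% | 9% |
| Stools only, 7-day mean | 16% | 4% | 1% |

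**Hand check of the zero-reference effect.** At 0.3 vomiting episodes/day, the chance of none in two reference days is exp(−0.6) = 0.549. The chance of at least one in seven later days is 1 − exp(−2.1) = 0.878. The product is 0.549 × 0.878 = 0.48. So 48% of subjects are flagged on vomiting merely because the reference was zero. That is well over half of the 79% flagged on vomiting alone under the any-day reading.

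**Sensitivity, stools only, any of 7 days.**

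- Stable Poisson counts: 69% at 3/day, 52% at 8/day, 41% at 12/day.
- Variance twice the mean: 76% at 3/day, 58% at 12/day.
- Lognormal measure: 0.3% at a within-subject CV of 0.1, 21% at 0.2, 65% at 0.5.

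**What a between-arm comparison gives.** If the same rule is applied to both arms, the expected difference with no product effect is 0 under any of these readings. With 61.4% flagged in each arm (stools 5/day, stable, any of 7 days), that is about 37 of 60 and 18 of 30. The 95% half-width is 1.96 × √[0.614 × 0.386 × (1/60 + 1/30)] = 1.96 × 0.109 = 0.21, or about 21 percentage points.

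**The case against.** The strongest reply is that section 9.1.4 does not state the rule that gives the high figures. It does not say any symptom, any day, seven days, or that a zero reference counts, and it can be read as a screen on events already recorded as adverse. These are treated inpatients, and section 8.4 works with durations of 2, 4 or 7 days without FMT, so falling counts are plausible and the rates are then lower. This stands. A reader might infer that the rule will label most FMT subjects as having a product-caused event, but the documents do not support that. It needs a permissive reading together with assumed rates.

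The consequences are also limited:

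- Section 9.2 provides a separate relatedness judgement, and nothing says that 9.1.4 overrides it.
- Section 8.5.4 plans no count of product-related events.
- Of the two halting rules in section 9.4, the one for serious related events also requires the event to be unexpected, and the other concerns infection. The expedited reports to the FDA in section 9.3 require unexpectedness too, whereas 9.1.4 lists expected events.
- Sections 3.2.3.2 and 3.2.3.3 name worsened diarrhea, nausea and vomiting as post-enrollment endpoints, so ordinary adverse event frequencies will exist for controls.

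None of this repairs the rule. Section 9.1.4 gives the threshold the purpose of distinguishing cause, and under every reading it lacks the comparison that would allow this. How it relates to the 9.2 judgement is not stated, in a trial where neither subjects nor investigators are blinded (section 5.6).

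**Conclusion.** The point holds as a flaw in a stated rule, and should be corrected. A 50% rise within a subject, with no concurrent reference, cannot separate product effect from disease course or chance. That conclusion follows from the text of 9.1.4 and needs no assumed rates.

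The size does need them. At 5 stools and 0.3 vomiting episodes per day, with independent Poisson days and no product effect, the false-attribution rate runs from about 1% to about 92% according to choices that the plan leaves open. The supportable statement is that the rate is uncontrolled and can exceed one half. It should not be said that most FMT subjects will be flagged, that the threshold alone settles causality, or that halting or expedited reporting depends on it.

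**What to change.** **Section 9.1.4.** Stop using the threshold as evidence of cause. Define one version with a fixed unit, fixed follow-up days and a stated rule for a zero reference. Base it on stool and emesis counts, which are the listed symptoms with planned daily recording in every arm. Apply it to all randomized subjects, with the reference window ending at randomization/enrollment and follow-up days counted from the same point in every arm, whatever the number of doses.

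**Section 8.5.4.** Report the proportion meeting the threshold by arm, with the FMT minus control difference and its confidence interval.

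**Section 9.2.** State that individual relatedness for these events comes only from this assessment.

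**Cost.** Wording changes, one more table and a short chart abstraction. Pre-randomization counts are not among the planned daily records, and Table 3 shows no symptom review at screening. The 7-day recording in section 3.1.5 runs from the final dose, so for subjects who are re-dosed some early days may also have to be abstracted. No new visits or measurements are needed. The limit is precision: at 60 v 30 the interval is roughly ±20 points, so only a large difference in common gastrointestinal symptoms would be clear.
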